5.2.1 Risk-Benefit Considerations

A benefit from contrast-enhanced LV EBD resulting in improved³⁶ diagnostic quality of echocardiographic examinations should be expected. Given the fact that the subjects to be enrolled in the present clinical trial will be already scheduled for echocardiographic examination but with suboptimal images and have no evidence of intracardiac shunts, inclusion in the study is not likely to add any risk for the subjects, since no particular safety concerns can be expected.

when administering LUMASON to children with respect to the safety profile of LUMASON. Furthermore, contrast enhanced transthoracic echocardiogram supposed to prevent the risk of those subjects being exposed to radiation through other imaging modalities in the downstreaming of appropriate assessment of cardiac structures.

5.3 Study Duration

The procedure associated with the investigational echo exam prior to and after the administration of the investigational product will be completed within approximately 15-30 minutes.

Safety monitoring will begin at the time of signing Informed Consent (and subject's "assent," according to requirements by local regulations), and will continue for 72 hours post dose.

5.4 Study Population

The study will be conducted in subjects who have sub-optimal images from transthoracic harmonic echocardiography. It is expected that approximately 7-12 study centers in the United States will participate in the study. Each site may enroll approximately 20 subjects in this trial. Approximately 92 subjects will be enrolled in order to obtain 73 evaluable subjects.

5.4.1 Inclusion Criteria

Enroll a subject in the study if they meet the following inclusion criteria:

- Is male or female, 9 to 17 years of age;
- Written informed consent is obtained from the subject's parent(s) or legal acceptable representative(s) (according to local regulations);
- Assent from the subject is obtained when applicable, that is, when it is required according to local regulations (IRB requirements) (see section 10.2);
- Is suspected of having cardiac disease or undergoing evaluation of cardiac anatomy for congenital heart disease;
- Has undergone a previous transthoracic echocardiogram within a one month period prior to enrollment in this study resulting in suboptimal LV EBD defined as ≥ 2 contiguous segments in any given view that cannot be visualized.

5.4.2 Exclusion Criteria

Exclude a subject from this study if the subject does not fulfill the inclusion criteria, or if any of the following conditions are observed:

- Children < 9 years of age;
- Has previously been enrolled in this study;
- Has been administered any other contrast agent either intravascularly or orally within 48 hours of the first LUMASON administration;

- Has known right-to-left, bidirectional or transient cardiac shunt, (ruled out with agitated saline study performed before administration of LUMASON) ;
- Has any known hypersensitivity to one or more of the ingredients of the investigational product (sulfur hexafluoride or to any components of LUMASON);
- Has received an investigational compound within 30 days before enrolling into this study;
- Is a pregnant or lactating female. Exclude the possibility of pregnancy in subjects who have started their menses (by testing on site at the institution (urine β HCG) within 24 hours prior to the start of investigational product administration);
- Is determined by the Investigator that the subject is clinically unsuitable for the study.

5.4.3 Discontinuation Criteria

Clearly document the reason for the subject's discontinuation on the Case Report Form. Discontinued subjects are not replaced. Discontinue a subject from the study if the subject:

- Withdraws consent/or assent if applicable;
- No longer meets the Inclusion Criteria;
- Experiences any of the Exclusion Criteria;
- Has an adverse event that, in the opinion of the Investigator, requires the subject's discontinuation. Perform patient follow-up in accordance with Section 8.1.5.

6 Investigational Product

The study investigational product (IP) is named LUMASON in the United States. The investigational product is supplied as a 3-part kit containing the following:

- clear glass vial labeled as LUMASON (sulfur hexafluoride lipid-type A microspheres) for injectable suspension,
- prefilled 5 mL syringe labeled as Sodium Chloride Injection, USP, 0.9% Sodium Chloride and its plunger rod
- Mini-spike

6.1 Description and Labeling

LUMASON is formulated as a 25 mg sterile, non-pyrogenic lyophilized powder in a septum-sealed vial. The gas phase in the vial is SF₆, an innocuous gas. The lyophilized powder is made of a combination of pharmaceutical grade polyethylene glycol (PEG) molecular weight 4000, phospholipids and palmitic acid. Phospholipids from chemical synthesis were selected for their higher chemical purity and lower pyrogenic potential.

A mixture of distearoylphosphatidylcholine (DSPC) and dipalmitoyl phosphatidylglycerol sodium (DPPG.Na) is used in the IP.

Following reconstitution, the injectable suspension contains 1.5 to 5.6 x 10⁸ microspheres/mL.

Table A: Description of Investigational Product

Ingredient	Concentration / Amount per Unit
Polyethylene glycol (PEG) 4000	4.91 mg/mL
Phospholipids (DSPC/DPPG 1:1 w/w)	0.075 mg/mL
Palmitic Acid	0.008 mg/mL
Sulfur Hexafluoride (SF ₆)	8 µL/mL

Investigational product will be supplied by Bracco. Labeling will be done according to the National Legal requirements of each country where the study may be conducted. Each vial will bear a two-part label, the second part of which once used will then need to be affixed to the appropriate page of the Case Report Form (Appendix A).

6.2 Storage

Store unused LUMASON vials in a secure area with limited access at controlled room temperature at 25°C (77°F), excursions are permitted to 15-30 °C (59-86°F)

6.3 Blinding and Randomization

This is an open-label, non-randomized study.

6.4 Handling and Preparation

Prior to administration, the lyophilized powder should be reconstituted with 5 mL of sterile 0.9% w/v sodium chloride solution to give a final concentration of 8µL of SF₆ lipid microspheres per mL. After adding the sodium chloride solution, the vial should be shaken vigorously for 20 seconds, after which a homogeneous white milky liquid is obtained. A detailed instruction for the reconstitution of LUMASON is presented in (Appendix B).

Once reconstituted, LUMASON can be left at room temperature. The suspension is usable for up to 3 hours, upon standing for more than 15 minutes, buoyancy causes some of the larger microspheres to rise to the surface. Therefore, gently agitate the reconstituted LUMASON vial in a top-to-bottom manner to resuspend the sulfur hexafluoride lipid microspheres before administration. The desired volume of the product is then withdrawn into a syringe for administration to the subject.

In the case of incomplete use of vial contents, the product cannot be reused.

6.5 Administration

Once reconstituted, LUMASON will be administered intravenously as a single 0.03 mL/kg bolus injection during echocardiography. The LUMASON injection will be followed immediately with 5 mL of saline to flush the intravenous line of any remaining contrast agent.

6.6 Accountability

In accordance with International Conference of Harmonization (ICH) and United States FDA requirements, the Investigator and/or Drug Dispenser must at all times be able to account for all IP furnished to the institution. The appropriate site personnel must sign, date and immediately forward to the Sponsor the IP receipt form included with each shipment.

No IP is to be used outside of this study. Record the use of the IP on the appropriate Drug Accountability Record. All containers of IP must be accounted for, whether used or unused, during the course of and at the conclusion of the study. At the conclusion of the study, all shipments of unused IP to the Investigator must be returned to the Sponsor accompanied by a completed, signed copy of the appropriate IP inventory reconciliation form.

7 Methodology

7.1 Study Schedule

Table B: Study Schedule

	Pre dose			Post dose				
	Within -24 h	Within -30 min ^e	Prior to IP administration	0 min	5 min	30 min	24 h	72 h
Written Informed Consent^a	×							
Adverse Events Monitoring^b	×	⇒	⇒	⇒	⇒	⇒	⇒	×
Concomitant Medications^c	×	⇒	⇒	⇒	⇒	⇒	×	× ^f
Medical History	×							
Physical Examination	×						×	
Vital Signs		×			×	×	×	
Pregnancy Test (if necessary)	×							
Pulse Oximetry/ ECG monitoring^d		×	⇒	⇒	⇒	×		
Laboratory Evaluations	×						×	
12-Lead Electrocardiogram		×				×	×	
IP Administration				×				
Unenhanced Echo			×					
Contrast Enhanced Echo				×				

a Obtain prior to implementation of any study procedure.

b Start monitoring from the time Informed Consent is given up to 24 h post dose and continue monitoring up to 72 hrs post dose through a telephone call placed at Day 3. Only post dose events will be tabulated as adverse events.

c For any subject where sedation is administered, record the sedation medication on the concomitant page of the CRF and indicate for sedation.

d Continuous pulse oximetry and ECG monitoring will be performed 30 min prior through 30 minutes following IP administration for all subjects suffering from pulmonary hypertension or unstable cardiopulmonary conditions.

e For any subject where sedation is administered, obtain a second vital sign series and ECG immediately before the echocardiography exam and after the sedation drugs have been administered.

f Record any new medication taken for treatment of an adverse event that occurred after the signed informed consent was obtained through 72 hours following IP administration.

Note: A subset of 12 subjects will undergo additional blood draws for analysis of SF₆ concentrations, (see Section 7.6).

7.2 Written Informed Consent

Obtain written Informed Consent from the subject's parent(s) or legal acceptable representative(s) (according to local regulations) prior to the implementation of study procedures required by the protocol. Obtain written Assent from the subject, when it is required by local IRB. Give to the subject's parent (s) or legal acceptable representative(s) a copy of the signed

and dated written informed consent form including any other written information regarding the study. Document Informed Consent process (Assent when applicable) in detail, in the source record at the site.

Separate written Informed Consent (Assent when applicable) is needed for those subjects who participate in the Pharmacokinetic subset.

7.3 Subject Numbering

Assign a 4-digit subject number for each subject who qualifies for the study and signs the written Informed Consent. The first two digits of the subject number will be the investigational site number assigned by Sponsor. For site numbers less than ten use a leading zero. The third and fourth digits will be a number starting with 01 for the first subject enrolled and incrementing by "1" for each sequential subject.

For example, at site 01, the investigative site will assign the first subject 0101; the second subject 0102, etc.

Never reassign subject numbers. In the event that a subject withdraws from the study, the number assigned to that subject is retired and the next subject receives the next sequential number.

7.4 Subject Evaluations

7.4.1 Medical History

Obtain a complete medical history after the subject has signed the Informed Consent and within 24 hours prior to IP administration. Record the subject's medical history on the Medical History section of the Case Report Form.

7.4.2 Pregnancy Test

If the subject is female, and of child bearing potential, exclude the possibility of pregnancy by testing (urine β HCG) within 24 hours prior to the start of IP administration.

7.4.3 Concomitant Medications

Record all medications (prescription and over-the-counter) taken within 24 hours prior to IP administration in the Concomitant Medication section of the Case Report Form. Record newly prescribed pharmacological treatments in this section from within 30 minutes prior to IP administration up through 24 hours post investigational product administration. Additionally, any new medication taken for treatment of an adverse event that occurred after the subject signed informed consent through 72 hours following IP administration should be recorded.

7.4.4 Safety Assessments

7.4.4.1 Adverse Events

Monitor subjects for any untoward medical events from the time of signed Informed Consent through 72 hours after investigational product administration.

Subjects will be evaluated at up to 72 hours post dose either by telephone call made by a healthcare professional, or by a scheduled, follow up visit.

Record all untoward medical events in the Adverse Event section of the Case Report Form as specified in Section 8. Only post dose untoward medical occurrences will be tabulated as adverse events.

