Adverse event (AE) collection begins when a subject signs the Informed Consent and continues through the follow-up period defined in the Section 7.4.4.1 “Adverse Events” of the protocol. In addition, an investigator should report any serious AEs that occur after this time period that he/she believes may be related to the IP.

Any untoward medical occurrence that occurs from the time of signed Informed Consent to the time immediately prior to investigational product administration will be tabulated in the Clinical Trial Report as a “pre dose event.”

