9.5 Safety Analysis

The safety data will be summarized for all subjects dosed. Summary tables, including change from UEUS to CEUS or clinically significant changes where applicable, will be presented for the following safety endpoints:

- Adverse Events
- Clinical Laboratory Evaluations
- Electrocardiograms
- Pulse Oximetry
- Vital Signs

All adverse events will be coded by MedDRA and summarized by system organ class and preferred term, by intensity and by causal relationship to the investigational product.

Only those occurrences which occur from the start of IP administration through the follow-up period defined in the protocol will be tabulated in the Clinical Trial Report as “adverse events” See Section 8.1.1.

Physical examination results, concomitant medication data will be presented in the data listings.

Summary statistics will be presented for volume of investigational product administered.

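### The closing safety contact has a latest time but no earliest time, so it can be made before the 72-hour adverse-event window ends, and no later contact is scheduled

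*Combined protocol and SAP*

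**What the plan says.** **The window.** Section 5.3 says safety monitoring "will continue for 72 hours post dose". Section 7.4.4.1 requires monitoring "from the time of signed Informed Consent through 72 hours after investigational product administration". The opening of section 8 says collection "continues through the follow-up period defined in the Section 7.4.4.1", so section 7.4.4.1 defines the follow-up period.

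**The closing contact.** Section 7.4.4.1 then states: "Subjects will be evaluated at up to 72 hours post dose either by telephone call made by a healthcare professional", with a scheduled follow-up visit as the alternative. Table B footnote b (section 7.1) tells sites to "continue monitoring up to 72 hrs post dose through a telephone call placed at Day 3". In the grid, the row "Adverse Events Monitoring" ends with a mark in the 72 h column. No section defines Day 3, gives an earliest time for the contact, or schedules a later one.

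**What else is collected after 24 hours.** In Table B, physical examination, vital signs, laboratory tests and 12-lead ECG all end by 24 h. Only adverse events and medication given for them (footnote f; section 7.4.3) reach the 72 h column.

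**Tabulation.** Section 9.5: "Only those occurrences which occur from the start of IP administration through the follow-up period defined in the protocol will be tabulated" as adverse events.

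**The concern.** After the 24-hour visit, a single contact is the only scheduled occasion to ask about new events. Section 8.1.4 describes collection by non-leading questions and examination, so hours that fall after the contact are not actively asked about. If the contact precedes hour 72, active follow-up is shorter than the stated window and may differ between subjects and sites. An early contact can lose events but cannot add any, so the error runs in one direction.

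Safety data are a secondary objective (section 4), and the introduction notes that contrast safety has not been definitively established in children. The exposed data are new non-serious events in the final hours, and medication taken for them, for which the plan has no other scheduled source.

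**Working it through.** The only figure involved is the 72-hour window. It is a fixed design value, so there is nothing to reproduce. The check compares the passages and then does clock arithmetic.

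**Comparing the timing statements**

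| Place | Timing | Earliest time given? |
|---|---|---|
| Section 5.3 | Monitoring for 72 h post dose | Not applicable (duration) |
| Section 7.4.4.1, monitoring duty | Consent through 72 h | Not applicable (duration) |
| Section 7.4.4.1, closing contact | Up to 72 h | No |
| Table B grid | 72 h column | Nominal time, no tolerance |
| Table B footnote b | Day 3 | No; day count undefined |

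The two sentences that tell a site when to make the contact both leave room for it before hour 72.

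**Inputs and formulas**

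- Window: 72 h (sections 5.3 and 7.4.4.1).
- Assumption, not in the documents: dosing and calls both take place between 08:00 and 18:00.
- Dosing day = Day 0: hours post dose at the call = 72 + (call clock time − dosing clock time).
- Dosing day = Day 1: hours post dose at the call = 48 + (call clock time − dosing clock time).
- Hours uncovered = max(0, 72 − hours post dose at the call).

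**Dosing day = Day 0**

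- Earliest: 72 + (8 − 18) = 62 h. Uncovered: 72 − 62 = 10 h, and 10/72 = 14% of the window.
- Latest: 72 + (18 − 8) = 82 h. Uncovered: 0 h.

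**Dosing day = Day 1**

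- Earliest: 48 + (8 − 18) = 38 h. Uncovered: 72 − 38 = 34 h, and 34/72 = 47%.
- Latest: 48 + (18 − 8) = 58 h. Uncovered: 72 − 58 = 14 h, and 14/72 = 19%.

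**One example.** A subject is dosed at 14:00 and called at 09:00 on Day 3. With the dosing day as Day 0, the call falls at 72 + (9 − 14) = 67 h, leaving 5 h uncovered. With the dosing day as Day 1, it falls at 48 + (9 − 14) = 43 h, leaving 29 h uncovered (29/72 = 40%).

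**Which day count fits better.** Table B counts elapsed time from 0 min to 24 h and 72 h. Footnote b makes the Day 3 call the means of monitoring up to 72 h. A call at 38 to 58 h could not do that, so Day 0 is the more natural reading.

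**After the fix.** A contact at or after 72 h leaves max(0, 72 − 72) = 0 h uncovered.

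The documents give no adverse-event rate by time since dosing, so uncovered hours cannot be turned into a number of missed events.

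**The case against.** The strongest reply is that the plan, read as a whole, already means 72 hours. The monitoring duty runs through hour 72, section 5.3 repeats it, and Table B marks the assessment in a 72 h column. A site that calls at 43 hours and then stops monitoring does not meet those provisions, so a reader should not infer that such a call is plainly compliant. This stands, and it makes the Day 1 figures a worst case. It does not close the gap: even with the dosing day as Day 0, afternoon dosing and a morning call leave some hours unasked.

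Serious events are also protected. Section 8.1.2 has them reported when the investigator becomes aware of them within the window. After the window, section 8 says "an investigator should report any serious AEs that occur after this time period that he/she believes may be related to the IP". Events already identified are followed to resolution or stabilisation (section 8.1.5). This stands too, and it confines the exposure mainly to new non-serious events that nobody volunteers.

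Finally, the practical effect is probably small. Safety is a descriptive secondary objective in a single-group study, so no between-group comparison can be biased. Section 5.2 cites 80% to 90% elimination by 11 minutes. Both facts bear on severity, but neither supplies an earliest time for the contact.

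**Conclusion.** The point holds as a minor but real weakness in a stated timing rule. The closing contact can precede hour 72, and nothing scheduled afterwards asks about the remaining hours. The likely size is about 0 to 10 hours (0% to 14% of the window), given the dosing day as Day 0 and the assumed 08:00 to 18:00 hours. The range of 14 to 34 hours depends on the dosing day being Day 1, which fits Table B less well.

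Two stronger readings are tempting but not supported:

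- A reader might infer that late events will go uncollected. The text permits that loss but does not make it certain, because calls may fall at or after 72 hours and events may be reported spontaneously.
- A reader might infer that the tables present ascertainment as complete through 72 hours. Section 9.5 says which events count as adverse events and makes no claim that all of them were captured.

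Sample size, power, type I error and the efficacy endpoints are not affected.

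**What to change.** Reconcile section 7.4.4.1 with Table B and its footnote b under one rule:

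- Make the closing contact, by call or visit, at or after 72 hours post dose, with a short upper window. An interval of 72 to 96 hours is one workable choice.
- Define Day 3 to match (dosing day = Day 0, allowing for the upper window), or drop the day label and use elapsed hours.
- Have the contact ask about all events and adverse-event treatments from the 24-hour visit to hour 72. Section 8.1.4 already records onset date and time, so anything starting after hour 72 can be separated.
- Record the contact's date and time, if the CRF does not already do so (it is not among the documents), and summarise actual contact times with the adverse-event tables.

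The cost is a wording change in two places and no extra contact. Some calls will come slightly later or fall due on a weekend, which the upper window is there to absorb.

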7.4.4.2 Physical Examination

Perform a physical examination within 24 hours prior to IP and at 24 hours after IP administration.

7.4.4.3 Vital Signs

Collect the following vital signs within 30 minutes pre dose and at 5 minutes, 30 minutes and 24 hours post dose. Obtain the following vital signs in a position that is consistent for all time points for each subject:

- Systolic blood pressure (mmHg)
- Diastolic blood pressure (mmHg)
- Heart rate (beats/minute)
- Respiratory rate (breaths/min)

7.4.4.4 Laboratory Evaluations

Collect blood samples within 24 hours prior to the investigational product administration and 24 hours after the IP administration. A central laboratory will perform evaluations for the analytes listed in Table C.

Table C: Laboratory Analytes

Hematology	Clinical Chemistry	
Hematocrit	Sodium	AST/SGOT
Hemoglobin	Potassium	ALT/SGPT
RBC count	Chloride	Alkaline Phosphatase
WBC count	Glucose	GGT
differential WBC count	Urea Nitrogen	Uric Acid
Platelets	Creatinine	Total Protein
PT	Total Bilirubin	Albumin
APTT	LDH	Calcium

Prepare blood and ship via overnight courier per the Instruction Manual provided by the central laboratory.

7.4.4.5 Electrocardiograms

A 12-Lead Electrocardiogram (ECG) will be performed in all subjects within 30 minutes prior to IP administration, and at 30 minutes and 24 hours after IP administration and a copy of the ECG report will be affixed to the CRF.

The ECG examinations will be evaluated by a central ECG laboratory that will provide the ECG equipment to the site and will employ a cardiologist to perform the centralized ECG evaluation containing the following information:

- RR interval
- PR interval
- QRS interval
- QT and QTc interval (Bazett's and Fridericia's)
- Overall diagnostic assessment
- Comparison to Baseline

